66 whole genome and/or whole transcriptome sequencing are able – by virtue of painting a more
67 delicate genetic portrait of a tumor sample – to provide a more accurate diagnosis.
68 To this end we generated a reference collection of 5,500 samples with the full spectrum of
69 hematological malignancies, for which we performed whole-genome sequencing as well as
70 whole-transcriptome sequencing. Moreover, gold standard diagnoses according to WHO
71 classification with all needed techniques, all performed in MLL, clinical data and therapy
72 response data are fully available for these cases. The main advantage of this reference

73 collection consists of the unambiguity of each diagnosis, providing a reference framework for
74 any further classification and diagnosis especially in difficult cases.

75 Therefore, SIRIUS will compare the diagnostic superiority of WGS or WTS to the combined
76 approach with gold standard results and by matching the obtained results to the nearest “digital
77 sibling” within our reference cohort of more than 5,500 WGS and WTS (both in 93% of cases).

78 To this end, we will use an inhouse developed matching algorithm, which is able to match
79 genomic or transcriptomic profiles to a group of similar cases and gold standard results from
80 timepoint of this study. Current workflows intended to generate WTS/WGS data from patient
81 samples – all while fulfilling state of the art accreditation (ISO 15189) – require up to 5 – 7
82 days. This is largely comparable to classical methods but holds the promise to replace error
83 prone and arduous iterations in the methodological work up. The objective is to test whether
84 WTS and/or WGS based approaches can surpass classical methods regarding diagnostic
85 precision and routine reliability. Here we will test this hypothesis in a prospective real-world
86 setting under diagnostically difficult circumstances.

87 **II. STUDY DESIGN**

88 1. Type of Study

89 SIRIUS is conducted as a monocentric prospective case-control study. The study population
90 consists of carefully chosen patients with potential hematological malignancy, for which
91 current diagnostic methods were not sufficient to provide clear-cut diagnosis and definitive
92 clinical guidance. SIRIUS is entirely a non-interventional study without therapeutic
93 consequences for direct patient care. Data will be used as research study and micro-cost
94 analysis will be provided.

95 2. Duration of Study

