96 SIRIUS will be conducted for a total number of 110 patients with inconclusive diagnosis by
97 gold standard techniques for a total of up to nine months after the first enrollment. Patients to
98 qualify for study will be selected by referring center and PI before material is send to MLL.

99 3. Quality Control

100 Due to the heterogeneity in quality of blood and bone marrow samples arriving at MLL,
101 SIRIUS is preceded by a rigorous quality assessment of every patient history, data already
102 available and sample source and quality to be potentially included in the present study. The
103 minimal requirements are listed in III.

104 4. Primary Study Endpoints

105 Overall, the efficacy and supremacy of WGS/WTS analysis will be subjected to current
106 standard procedures. The primary endpoint will be assessed as follows: unclear cases will be
107 subjected to three diagnostic algorithms:

108 (1) Inhouse at referring site by histopathological diagnosis in the context of a hematological
109 tumor board according to current standards (“best practice”)

110 (2) Current gold-standard diagnostic workup as performed routinely by the MLL,
111 consisting of

112 a. Cytomorphological diagnosis
113 b. Immunophenotypic diagnosis
114 c. Chromosomal banding analysis
115 d. Molecular testing
116 e. NGS based Targeted panel sequencing

117 (3) WGS and WTS sequencing plus matching to nearest digital sibling in 5,5k cohort

118 The results of (2) and (3) arms will be first compared to the result obtained in (1) since this is
119 the therapy guiding approach *in domo*. Clinical follow-up observations will be made to assess
120 the success of this first diagnosis.

121 Next results from (2) and (3) will be compared against each other to obtain an assessment of
122 replaceability of current gold-standard methods to either WGS or WTS and WGS/WTS
123 combined. If both approaches do not yield a similar conclusion, specific data from (2) will be
124 added to results in (3) until a definitive assessment can be made.

125 5. Secondary Study Endpoints

126 • Turn-over time until potential therapy guiding diagnosis
127 • Cost-effectiveness until timepoint of diagnosis and therapy
128 • Compare WES to WGS data in SIRIUS cohort
129 • Identify number of potential actionable targets for which a therapy has been approved
130 but identification was missed in (1) and (2)
131 • Identify putative disease stage in comparison to (2) and clinical history

132

133

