134 **III. SUBJECT SELECTION AND WITHDRAWAL**

135

136 1. Number Of Subjects

137 SIRIUS intends to enroll a total number of 110 cases provided by approximately 50 certified
138 hematological centers.

139

140 2. Gender, Age

141 Patients' samples from both sexes will be used (male and female). Only samples from adult
142 patients (18 years or older) will be used.

143

144 3. Inclusion Criteria

- 145 • Patients having been investigated with a suspected hematological disorder and:
 - 146 ○ Having unclear diagnosis after internal routine diagnosis
 - 147 ○ Unusual clinical course
 - 148 ○ Unusual r/r status or non-responder
 - 149 ○ Multiple parallel hematological conditions
 - 150 ○ Difficult/rare therapy associated/secondary neoplasms
- 151 • Current diagnostic work-up is not satisfactory in terms of (1) accuracy (2) clinical
152 behavior
- 153 • Only samples of patients min. 18 years of age will be used
- 154 • Material with a minimum of 20% tumor content in bone-marrow or peripheral blood
155 sample
- 156 • Samples must suffice quality attributes control which are denoted in (4.)
- 157 • Patient's informed consent

158 4. Exclusion Criteria

159 • Sample is not fit for state-of-the-art diagnosis, fails initial quality control. For quality
160 insurance we will exclude samples with wrong anticoagulant sent. Samples with
161 damage due to meteorological reasons (freeze-thaw damage or elevated temperature)
162 will be excluded.

163 • Samples with too scarce material jeopardizing routine gold-standard diagnosis will be
164 excluded (tumor content < 20 %).

165

166 5. Location

167 SIRIUS will be conducted as monocentric trial at the MLL.

168 **IV. STATISTICAL PLAN**

169

170 To determine the statistical significance within the endpoint analysis we will assess both
171 quantitative as well as qualitative variables. Quantitative variables will be described with the
172 number of non-missing values, mean, standard deviation, median, and minimum/maximum
173 values. Qualitative variables will be expressed as a number and percentage of patients with
174 each qualitative characteristic. The missing values are not intended to be included in the
175 calculation of percentages. Sensitivity and specificity will be assessed specific to each method,
176 with respect to internal gold standard diagnostic work-up.

177

178 **V. RISKS AND BENEFITS**

179 *Potential Direct Benefits to Subject*

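### Section IV promises statistical significance but fixes only per-method summaries and accuracy against comparator (2), so it cannot show that WGS/WTS is superior to (2)

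*Protocol*

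**What the plan says.** Section IV (Statistical Plan) states its purpose first: "To determine the statistical significance within the endpoint analysis we will assess both" quantitative and qualitative variables. The methods that follow are:

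- for quantitative variables, "number of non-missing values, mean, standard deviation, median, and minimum/maximum" values;
- for qualitative variables, "Qualitative variables will be expressed as a number and percentage of patients with" each characteristic;
- for missing data, "The missing values are not intended to be included in the" calculation of percentages;
- for accuracy, "Sensitivity and specificity will be assessed specific to each method", "with respect to internal gold standard diagnostic work-up".

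Two other sections set what these methods have to deliver. Section I.2 (Objectives) says "SIRIUS will compare the diagnostic superiority of WGS or WTS to the combined" approach with gold standard results, and presents this as a hypothesis that the study will test. Section II.4 (Primary Study Endpoints) puts the unclear cases through three algorithms: (1) the referring site's diagnosis, (2) the MLL gold-standard work-up, and (3) WGS and WTS with matching to the reference cohort. Algorithms (2) and (3) are each compared with (1). Then "Next results from (2) and (3) will be compared against each other to obtain an assessment of" whether the current methods could be replaced. If (2) and (3) disagree, data from (2) are added to (3) until an assessment is reached.

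**The concern.** The stated purpose and the stated methods do not match. Counts, percentages, means and standard deviations for each method do not test or estimate a difference between methods. Because the same patients go through (2) and (3), the evidence that one resolves more cases than the other lies in two counts: patients resolved only by (3) and patients resolved only by (2). Two separate percentages fix the difference between these counts, but not the counts themselves, so they do not fix the precision of the comparison.

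The sensitivity and specificity sentence does cross-classify (3) against (2), but it makes (2) the truth. A case that (3) resolves and (2) does not, which is the event that would support superiority, is then scored as an error of (3).

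The missing-value rule adds a smaller problem: the percentages for (2) and (3) may rest on different patients. What is at stake is the study's main claim, that sequencing surpasses classical methods. Section IV, followed to the letter, yields no figure that could establish it.

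**Working it through.** **No figure of the plan to reproduce.** The protocol gives no significance level, power, effect size or resolution rate.

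**Inputs.** N = 110 is from the protocol (II.2 and III.1). Assumed, for illustration only: a binary outcome (diagnosis resolved or not), with (2) resolving 55/110 = 50% and (3) resolving 66/110 = 60%; two-sided level 0.05.

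**Notation.** b = resolved by (3) only; c = resolved by (2) only. The percentages fix b − c = 66 − 55 = 11, and c may vary.

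**Formulas.** Exact McNemar p = 2 × P(X ≤ c), with X ~ Binomial(b + c, 0.5). Paired difference = (b − c)/N, with Wald standard error √(b + c − (b − c)²/N)/N.

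| b vs c | resolved by both (55 − c) | exact McNemar p | difference, points (Wald 95% CI) |
|---|---|---|---|
| 11 vs 0 | 55 | 2 × 0.5¹¹ = 0.001 | 10 (4.4 to 15.6) |
| 18 vs 7 | 48 | 0.043 | 10 (1.3 to 18.7) |
| 19 vs 8 | 47 | 0.052 | 10 (0.9 to 19.1) |

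For 18 vs 7, the standard error is √(25 − 121/110)/110 = √23.9/110 = 0.0444, and 1.96 × 0.0444 = 0.087.

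In the 19 vs 8 row the simple Wald interval just excludes zero while the exact p is above 0.05. The interval method therefore has to be stated too.

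**Are these splits plausible?** If the methods were statistically independent, 110 × 0.5 × 0.6 = 33 patients would be resolved by both. All three rows have 47 or more, so all show positive association, as one expects of two methods applied to the same patient.

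**What sensitivity and specificity show when (2) is the reference.** Sensitivity of (3) = (55 − c)/55; specificity = (55 − b)/55.

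- 11 vs 0: sensitivity 55/55 = 100%, specificity 44/55 = 80%.
- 18 vs 7: sensitivity 48/55 = 87%, specificity 37/55 = 67%.

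In the first case (3) resolves everything that (2) resolves and 11 cases more, and the measure charges those 11 as false positives. A perfect score on both measures needs b = c = 0, that is, results identical to (2). A method scored this way can at best equal its reference.

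**The case against.** **Within-patient comparison is already planned.** II.4 announces it, and its rule for disagreements requires discordant cases to be identified one by one. This stands: the comparison is not absent from the protocol. What is lacking is a statistic for it in the section said to determine significance.

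**The discordant counts could be recovered.** With a binary outcome and counts reported, sensitivity and specificity give them back: 48/55 and 37/55 return c = 7 and b = 18. This also stands, so it would be wrong to infer that Section IV holds nothing but one-sample summaries or that all pairing information is lost. Recoverable is not the same as analysed, however, and the measure as stated counts b against (3).

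**Naming a test belongs in an SAP.** True, and the point does not rest on a missing test name. It rests on a section that states a purpose and fixes methods that do not serve it.

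**Stronger readings that the documents do not support:**

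- A reader might infer that an unpaired test with the wrong standard error is planned. No such test appears.
- A reader might infer that, for any pair of percentages, the evidence could range from overwhelming to absent. The extremes need implausible overlap. With 44 vs 60 resolved of 110 (assumed), independence gives 44 × 60/110 = 24 resolved by both, a split of 36 vs 20 and p = 0.044. Any positive association gives a smaller p. The p = 0.14 at 60 vs 44 needs no patient at all to be resolved by both methods.
- The assumed rate for (2) has no source. II.2 enrols patients whose gold-standard diagnosis was inconclusive. Since c cannot exceed the number that (2) resolves, a low rate for (2) leaves little room for c to vary, and the ambiguity shrinks.

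**Time and cost.** On complete pairs, the difference of means equals the mean within-patient difference. Only its precision is lost, and these endpoints are secondary.

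**Conclusion.** The mismatch is real and lies within the protocol. Section IV aims at statistical significance, I.2 aims at superiority, and the methods fixed in Section IV cannot show (3) superior to (2).

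The accuracy part rests on reading the internal gold standard as algorithm (2), which II.4's label supports. If another work-up were meant, that part would change, but the paired difference between (2) and (3) would still be neither tested nor estimated.

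The size depends on assumed rates. At 50% vs 60% of 110, the exact p runs from 0.001 (11 vs 0) to 0.052 (19 vs 8) among splits that all show positive association. With other rates, the percentages may leave the conclusion in less doubt.

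This is a should-fix. Patient-level pairing is retained in the data, so a proper analysis remains possible.

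**What to change.** In Section IV:

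1. Define a per-patient binary outcome (diagnosis resolved, yes/no) by one rule applied alike to (2) and (3).
2. For (3), use the result recorded before any data from (2) are added under II.4.
3. Cross-tabulate (2) against this unaided (3) in patients with both results. Report both discordant counts, the paired difference with a 95% CI by a stated method for matched proportions, and an exact McNemar test.
4. Report agreement of (3) with (2) as concordance only, not as accuracy. Keep the descriptive statistics as supporting summaries.
5. As a secondary refinement, report within-patient differences with a 95% CI for turn-over time and cost.

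The cost is a revised Section IV, some extra analysis work and agreement on the resolved/unresolved rule, which is the harder part because II.4 compares diagnoses without defining such an outcome. No additional patients are needed, but the unaided result of (3) must be recorded before the II.4 step.

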30 to classical methods. In SIRIUS we will prospectively challenge this hypothesis to address the
31 question of how often a better or final diagnosis can be delivered by WGS and/or WTS and if
32 unclear cases can be efficiently resolved.

33

34 **Type of Research:** observational study, diagnostic study, hematology, leukemia, next
35 generation sequencing

36

37 **Intervention:** none

38 **APPROVAL**

39 This study will be conducted with the utmost respect for individual patients in accordance with
40 the requirements of this diagnostic trial protocol and especially in accordance with the
41 following:

42 • Good clinical practice directive (European Union) (2005/28/EC)

43 • The ethical principles in accordance with the Declaration of Helsinki

44 • International Conference on Harmonization (ICH) E6 Good Clinical Practice:
45 consolidated guideline

46 • Guidelines for Good Clinical Practice (*Deutsche Forschungsgemeinschaft DFG*)

47 • Standards and guidelines for the interpretation of sequence variants (PMID: 25741868)

48 • All applicable laws and regulations, including, without limitation, data privacy laws,
49 clinical trial disclosure laws, and regulations.

50 **I. INTRODUCTION**

51 1. Background and Rationale

52 Treatment of hematological diseases relies on a single cardinal prerequisite: correct
53 classification within the broad specter of malignant diseases arising from the hematopoietic
54 system. With the ever-expanding availability of distinct yet complementary diagnostic tools,
55 our understanding of the landscape of hematological diseases steadily increases. As such, the
56 current consensus classification as summarized through the WHO classification (2017)
57 represents a compass guiding diagnostic algorithms to the correct diagnosis. Today, the gold
58 standard of routine diagnostic process relies on five methodological pillars: cytomorphology,
59 histology, chromosomal cytogenetics, immunophenotyping, and molecular genetic testing.
60 This leads to a treatment enabling diagnosis in the vast majority of cases. However,
61 approximately 10 % of cases remain unresolved from a diagnostic point of view and hence do
62 not lead to a satisfactory diagnosis according to current WHO standards (2017). We intend to
63 solve this issue to provide illuminating diagnostic guidance for the best possible patient's care.

64 2. Objectives

65 To address this problem, we hypothesize that novel high throughput sequencing methods, e.g.,

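### Section IV leaves missing values out of every percentage; if a sample with no WGS or WTS result is treated as missing, the proportion of cases resolved is inflated by the factor N/(N-m)

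*Protocol*

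**What the plan says.** Section IV (Statistical Plan) begins with the endpoint analysis: "To determine the statistical significance within the endpoint analysis we will assess both" quantitative and qualitative variables. Qualitative variables are to be given as counts and percentages of patients. The next sentence sets the rule: "The missing values are not intended to be included in the" calculation of percentages. No variable is exempted.

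Three other places show what the percentages are for:

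- The research question in the opening summary is the "question of how often a better or final diagnosis can be delivered by WGS and/or WTS and if" unclear cases can be resolved.
- Section I.2 (Objectives) sets out to test whether sequencing surpasses classical methods on diagnostic "precision and routine reliability. Here we will test this hypothesis in a prospective real-world" setting.
- Section II.4 (Primary Study Endpoints) compares the gold-standard work-up (2) with sequencing (3) to assess the "replaceability of current gold-standard methods to either WGS or WTS and WGS/WTS" combined.

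Samples are filtered at entry by initial quality control and by a 20% minimum tumour content. Section III.4 also says "Samples with too scarce material jeopardizing routine gold-standard diagnosis will be" excluded. Section V gives current diagnostics first call on sample material. The protocol does not say how a sample is recorded if it passes these filters and then yields no sequencing result.

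**The concern.** Whether a strategy resolved a case is a qualitative variable. A sample with no sequencing output has no value for it, so on a plain reading the Section IV rule removes that sample from the denominator. Yet for a question about how often sequencing delivers a diagnosis, and how reliable it is in routine, that sample is a case the strategy did not resolve. Removing it hides the kind of unreliability the trial sets out to measure.

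The entry filters make such failures less likely but do not rule them out. The scarcity criterion and the priority for material both protect the gold-standard work-up, and nothing shown reserves material for sequencing. Failures could therefore fall more on (3) than on (2). If they did, the rule alone would favour sequencing in the comparison used to judge replaceability. A completed but inconclusive run is a result and is not at issue here.

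**Working it through.** The protocol has no calculated figure to reproduce: it gives no failure rate, expected yield, alpha or power.

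**Inputs**

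- N = 110 cases (Sections II.2 and III.1), taken here as the number whose sample passed initial quality control. If some of the 110 fail quality control, N is smaller and the effect of the same m is slightly larger.
- m = number of those with no result for the strategy. Not given; assumed 0, 2, 6 or 11.
- r = number resolved. Not given; assumed 33, 55 or 77, that is 30%, 50% or 70% of 110.

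**Formulas**

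- Failures counted as not resolved: r/N.
- Failures treated as missing: r/(N-m).
- Ratio of the second to the first: N/(N-m), whatever r is. Relative excess: m/(N-m). Absolute excess: (r/N) × m/(N-m).

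**WGS alone or WTS alone**

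| m | N/(N-m) | r=33 (30%) | r=55 (50%) | r=77 (70%) |
|---|---|---|---|---|
| 0 | 1.000 | 30.0% | 50.0% | 70.0% |
| 2 | 110/108 = 1.019 | 30.6% (+0.6) | 50.9% (+0.9) | 71.3% (+1.3) |
| 6 | 110/104 = 1.058 | 31.7% (+1.7) | 52.9% (+2.9) | 74.0% (+4.0) |
| 11 | 110/99 = 1.111 | 33.3% (+3.3) | 55.6% (+5.6) | 77.8% (+7.8) |

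**WGS/WTS combined**

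A case with one working assay still has a result, so m counts only double failures. With a WGS failures and b WTS failures, double failures range from 0 to the smaller of a and b. If failures are independent, a × b/110 are expected.

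- a = b = 6: 36/110 = 0.33 cases expected, an excess of 0.1 to 0.2 points over yields of 30% to 70%. If the same 6 samples fail both assays: 1.7 to 4.0 points.
- a = b = 11: 121/110 = 1.1 cases expected, an excess of 0.3 to 0.7 points. If the same 11 samples fail both: 3.3 to 7.8 points.

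Shared causes such as scarce or degraded material would push towards the upper figures.

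**Effect on the comparison with (2)**

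Suppose (2) has a result for every sample and both strategies resolve 55 of 110. With 11 WGS failures treated as missing, the table would show 55.6% for WGS against 50.0% for (2), a difference of 5.6 points made by the denominator alone.

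**Scale**

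The 95% half-width, 1.96 × sqrt(p(1-p)/110), is 8.6 points at 30% or 70% and 9.3 points at 50%. Every excess above is smaller than that, but sampling error goes both ways and this error goes only upward.

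**The case against.** The strongest reply is that the deciding step is not written down. Section IV says what happens to missing values, not that a failed assay is one. Coding could be settled in a statistical analysis plan that is not shown, or in the data management documents that Section VI says will describe analysis methods. If failures are coded as not resolved, the rule never touches them. This stands, and it is why the point is conditional. It does not remove the point: the rule is stated without exception in a section that opens with the endpoint analysis, and an exemption made elsewhere would depart from the protocol's text.

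It can also be said that:

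- **The sentence is generic descriptive text, and Section II.4 defines no proportion resolved.** Partly right. The proportion comes from the research question, and sensitivity, specificity and agreement between methods are properly left on their own denominators.
- **Yield among samples with a result is a legitimate quantity.** It is, as a secondary figure. It answers a different question from how often the strategy delivers a diagnosis. Counts are reported too, so a reduced total could be noticed, but the percentage would still be too high for that question.
- **Patients are selected before material reaches the laboratory (Section II.2).** This stands. Counting every selected patient could bring in samples rejected for the wrong anticoagulant or transport damage and pull the yield down. The denominator should start from samples that passed initial quality control.

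A reader might infer from Section I.2, where both assays are available in 93% of the reference cohort, that about 7% of assays fail. The protocol gives no reason for the gap, so it cannot serve as a failure rate. A reader might also extend the point to actionable targets, but Section II.5 plans these as a count ("Identify number of potential actionable targets for which a therapy has been approved"), which a rule on percentages does not affect.

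**Conclusion.** The point holds as a conditional one. As written, Section IV permits, and on a plain reading leads to, a denominator that drops samples with no sequencing result. If it is applied that way, the proportion resolved is multiplied by N/(N-m), always upward, relative to counting those samples as not resolved.

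The size is unknown. With N=110 and assumed yields of 30% to 70%, it runs from 0 points with no failures to 3.3 to 7.8 points with 11 failures of a single assay. For WGS/WTS combined it is well under 1 point if the assays fail independently at these rates, and reaches the single-assay figures only if the same samples fail both.

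A reader might go further and conclude that the trial will overstate sequencing yield, or that the comparison with (2) is biased. The documents do not support that. They give no failure rate, do not say failures are coded as missing, and do not say that (2) will have a result for every sample. The text should be changed, because the rule answers the trial's own question less well than a cheap alternative does.

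**What to change.** Replace the missing-value sentence in Section IV with text such as:

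> Missing values are excluded from percentages of descriptive variables only. For the proportion of cases resolved by (2), by WGS alone, by WTS alone and by WGS/WTS combined, the denominator is all enrolled patients whose sample passed the initial quality control in Section III. An assay with no result counts as not resolved for that strategy. For WGS/WTS combined, a case with one working assay is judged on that assay; the case counts as failed only if neither assay gives a result. The number of failures is shown by method. Percentages among evaluable samples are secondary. Sensitivity, specificity and between-method agreement keep their own denominators, with the number of failures shown beside them.

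No proportion resolved is needed for (1), because an unclear diagnosis after internal work-up is among the entry criteria.

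The cost is a few sentences and one small table. No extra samples are needed, but each assay's failure has to be recorded. The downside is that the reported WGS/WTS yield may be slightly less favourable, by 0 to about 8 points over the assumed range.

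### Section IV measures accuracy against what is most naturally the MLL work-up, so this analysis cannot show WGS/WTS to be more accurate than that work-up

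*Protocol*

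**What the plan says.** Section IV (Statistical Plan) gives one accuracy analysis: "Sensitivity and specificity will be assessed specific to each method", "with respect to internal gold standard diagnostic work-up". It names no other reference for these two measures.

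Section II.4 (Primary Study Endpoints) defines three algorithms:
- (1) is the referring site's diagnosis.
- (2) is the "Current gold-standard diagnostic workup as performed routinely by the MLL".
- (3) is WGS and WTS with matching to the reference cohort.

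The section opens with "Overall, the efficacy and supremacy of WGS/WTS analysis will be subjected to current" standard procedures. It compares (2) and (3) with (1), then with each other, to judge "replaceability of current gold-standard methods to either WGS or WTS and WGS/WTS" combined. Where (2) and (3) disagree, data from (2) are "added to results in (3) until a definitive assessment can be made". Clinical follow-up is planned to assess "the success of this first diagnosis", that is, the diagnosis from (1).

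Section I.2 (Objectives) asks whether WGS/WTS can outperform classical methods on diagnostic precision, and describes repeated rounds of the current work-up as prone to error. The opening summary asks how often sequencing gives a better or a final diagnosis. In section III.3 the word *internal* appears in another sense, in the inclusion criterion "Having unclear diagnosis after internal routine diagnosis".

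**The concern.** A reference standard is treated as the truth. If the reference is also one of the compared methods, that method cannot be wrong, and any method that improves on it is scored as worse. I.2 asks for exactly such an improvement over classical methods.

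The question of a *final* diagnosis concerns yield, and II.4 can answer it. The question of a *better* diagnosis needs a reference other than the method under challenge. As written, a reader could take sensitivity and specificity below 100% as evidence that WGS/WTS is less accurate than the MLL work-up, when the figures would partly reflect cases in which sequencing corrected it.

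**Working it through.** The protocol gives no assumed sensitivity, specificity or prevalence, so there is no figure of its own to reproduce. The main result is logical; the numbers only illustrate it.

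**Which work-up is the reference.** II.4 attaches the gold-standard label to (2) and describes (1) as best practice. The MLL is both sponsor (VIII) and study site (III.5). *Internal gold standard* therefore most naturally means (2).

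**Logical step.** Let R be the reference result. If R is the result of (2), then P((2) = R) = 1, so (2) has sensitivity and specificity of 100%. Method (3) reaches 100% only by agreeing with (2) in every scored case. A case in which (2) is definite and wrong and (3) is right is a disagreement, and counts against (3). A case in which (2) is inconclusive has no R.

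**The other reading.** If *internal* has its III.3 sense, the work-up before study entry, the reference is (1). That diagnosis was unclear at entry, and (1) is also one of the compared algorithms.

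**Illustration.** All inputs are assumed: a binary target, (2) definite in every case scored, a3 and a2 the true sensitivity = specificity of (3) and (2), prevalence p, and errors independent given true status.

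Apparent sensitivity of (3) = [p·a3·a2 + (1−p)(1−a3)(1−a2)] / [p·a2 + (1−p)(1−a2)]

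Apparent specificity of (3) = [(1−p)·a3·a2 + p(1−a3)(1−a2)] / [(1−p)·a2 + p(1−a2)]

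With a3 = 0.95, a2 = 0.80 and p = 0.5, sensitivity is (0.380 + 0.005) / 0.500 = 0.77, and specificity is the same by symmetry. With p = 0.2, sensitivity is (0.152 + 0.008) / 0.320 = 0.50 and specificity is (0.608 + 0.002) / 0.680 = 0.90.

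| True accuracy of (2), with (3) at 0.95 | (3) shown, p = 0.5 | (3) shown, p = 0.2 | (2) shown |
|---|---|---|---|
| 0.90 | 0.86 / 0.86 | 0.67 / 0.93 | 1.00 / 1.00 |
| 0.80 | 0.77 / 0.77 | 0.50 / 0.90 | 1.00 / 1.00 |
| 0.70 | 0.68 / 0.68 | 0.38 / 0.86 | 1.00 / 1.00 |

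**Without independence.** With error rates e3 = 0.05 and e2 = 0.20, overall agreement lies between 1 − (e3 + e2) = 0.75 and 1 − |e2 − e3| = 0.85. The same limits hold with several diagnostic categories: agreement is at least P(both right) ≥ 0.75, and at most 0.75 + 2 × 0.05. A true advantage of 0.95 − 0.80 = +0.15 would thus appear as a deficit of 0.15 to 0.25.

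**In cases.** If (2) were definite in all 110 and errors were independent, the expected counts are:
- both right: 110 × 0.95 × 0.80 = 83.6
- only (3) right: 110 × 0.95 × 0.20 = 20.9
- only (2) right: 110 × 0.05 × 0.80 = 4.4
- both wrong: 110 × 0.05 × 0.20 = 1.1

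Apparent agreement is (83.6 + 1.1) / 110 = 0.77. The 20.9 cases corrected by (3) are all scored as its errors.

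**The case against.** The strongest reply is that section IV does not make sensitivity and specificity the primary analysis. The primary endpoint in II.4 is a set of comparisons, and for replaceability the MLL work-up is a legitimate comparator. II.5 also counts actionable targets that (1) and (2) missed, which credits (3). And because IV speaks of each method, it can be read as ranking WGS, WTS, WES and the components of (2) against the composite, where the order is not fixed in advance. All of this stands and limits the point to (3) against (2) as a whole. For replaceability, however, the quantity is agreement and should carry that name.

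It may also be said that the details can be left to a statistical analysis plan. That holds for an unspecified detail, but here the protocol itself states the reference.

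Four stronger readings are tempting, and the documents support none of them:
- **The trial cannot show any benefit of sequencing.** The II.4 comparisons and the missed-targets endpoint can still show discordance and yield.
- **The reference is inconclusive in every patient.** II.2 does enrol patients whose diagnosis by gold-standard techniques is inconclusive, but it has them selected before material reaches the MLL. How often (2) then becomes definite is unknown.
- **A deficit of 0.15 to 0.25 is to be expected in this trial.** Those figures rest wholly on assumed inputs and apply only to cases where (2) is definite.
- **The planned follow-up could simply replace (2) as the truth.** II.4 ties it to (1), section V has state-of-the-art diagnosis and reporting for each sample, so results of (2) may shape later care, and no rule turns follow-up into a diagnosis.

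**Conclusion.** The point holds in a limited form. If the reference in section IV is (2), the sensitivity and specificity analysis cannot show that (3) is more accurate than (2) as a whole: the best possible result is a tie, and corrected diagnoses lower the score of (3). This conclusion is logical and does not depend on the illustrative figures. Its size in this trial cannot be derived from the protocol, because neither the true accuracy of (2) nor the share of cases in which (2) is definite is known.

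The conclusion depends on reading *internal gold standard* as (2). The alternative, (1), also gives an unsuitable reference, so the text needs correction either way. This should be fixed, but it does not invalidate the primary comparisons. Confidence is medium, because *internal* is undefined and IV also admits a method-by-method reading.

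**What to change.** In sections II.4 and IV:

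- (a) State which work-up *internal* refers to.
- (b) For replaceability, report (3) versus (2) as positive, negative and overall agreement, not as sensitivity and specificity.
- (c) Analyse the (3) result as recorded before any data from (2) are added under the II.4 disagreement rule.
- (d) For the question of a better or final diagnosis, report paired diagnostic yield, meaning a definite diagnosis by (2) and by (3), over all enrolled cases, with inconclusive cases as their own category. Limit the conclusion to agreement and yield.

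Follow-up may be shown descriptively for discordant cases. Besides the limits given above, it is short for late enrolees. Counting unverified cases in the denominator also pulls the (3) minus (2) difference towards zero. Continuing the assumed example with an error-free reference:

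| Cases verified (assumed) | Only (3) right v only (2) right | Difference over 110 (95% CI) |
|---|---|---|
| all | 21 v 4 | 17/110 = 0.155 (0.07 to 0.24) |
| about 75% | 16 v 3 | 13/110 = 0.118 (0.04 to 0.19) |
| about 50% | 10 v 2 | 8/110 = 0.073 (0.01 to 0.13) |

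The intervals narrow while the estimate shrinks, so this is attenuation and not a loss of precision.

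The cost is wording in two sections and one recorded (3) result per case before (2) data are added; no new samples or tests are needed. The price is that this analysis will support no claim of superior accuracy of (3) over (2).
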